intervention as well as pre-post multimodal evaluation. As for the quantification of changes in amyloid load, we will compare individual *relative standard uptake values* (SUVR) before and after tACS, according to established threshold values. PET Amyloid levels across brain regions will be quantified using standard uptake values normalized to uptake in the cerebellum (SUVR; (Lopresti et al., 2005)). Studies have suggested that the test-retest reliability of amyloid-PET measurement is high, with an intraclass correlation of 0.99, and a relative measurement error of 3% (C. R. Jack et al., 2013). Subjects will be defined as amyloid positive if the global (across all regions) cortical to cerebellar SUV ratio is greater than or equal to 1.6 (Clifford R. Jack et al., 2008). The annual rate of change in the global and regional amyloid ratio varies as a function of patient clinical status and baseline SUVR, but is generally either nonsignificant or small but positive, typically on the order of 0.05 units/yr, and asymptotes in patients with cognitive deficits and high amyloid levels (C. R. Jack et al., 2013; Clifford R. Jack et al., 2009; Villain et al., 2012; Villemagne et al., 2013), suggesting that major changes are unlikely over the short time period between baseline and post-intervention testing. Furthermore, significant decreases in amyloid (> 0.05 units/yr) are rare, particularly in patients with MCI/AD (C. R. Jack et al., 2013), suggesting that decreases above this magnitude would represent a reliable measure of tACS effect. Changes in SUVR will be evaluated by looking at individual trajectories of amyloid change (i.e. decrease in amyloid load or slowing of amyloid build-up) exceeding the threshold.

Data Analysis:

Changes in EEG metrics (e.g. gamma spectral power), amyloid beta levels, clinical and cognitive scores, as well as brain plasticity levels, will be measured using paired-sample t-test statistics, by applying a p.value < 0.05 . Details about computation EEG-based measures are described below.

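### A single patient's SUVR fall above 0.05 is treated as a reliable tACS effect without being compared with two-scan error; at SUVR 1.6, noise alone gives such a fall in 2% to 23% of unchanged patients, depending on what the quoted 3% means

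*Combined protocol and SAP*

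**What the plan says.** Under Sample Size Justification (B3.B), the plan compares each participant's SUVR before and after tACS against a threshold, and expects 5 or 6 fully characterised completers. The paragraph gives these facts:

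- Test-retest reliability is high, "with an intraclass correlation of 0.99, and a relative measurement error of 3" per cent.
- A patient is amyloid positive if the global "cortical to cerebellar SUV ratio is greater than or equal to 1.6".
- The natural yearly change is small and positive, "typically on the order of 0.05 units/yr", and it "asymptotes in patients with cognitive deficits and high amyloid levels".
- "significant decreases in amyloid (> 0.05 units/yr) are rare, particularly in patients with MCI/AD", "suggesting that decreases above this magnitude would represent a reliable measure of tACS effect".

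Response is then read from "individual trajectories of amyloid change (i.e. decrease in amyloid load or slowing of amyloid build-up) exceeding the threshold". The threshold is not named at that point. However, 1.6 is a positivity cut-off, and 0.05 is the only change value given and is tied directly to the claim of a tACS effect.

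Separately, Data Analysis says that changes in amyloid, among other measures, "will be measured using paired-sample t-test statistics" at the 0.05 significance level. That test does not use the 0.05 SUVR threshold.

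**The concern.** The plan infers that a fall is reliable because yearly falls of that size are rare. Reliability for one patient depends on a different quantity: the spread of the difference between two scans when nothing has changed. The paragraph contains the raw material for that comparison (the 3%) but never makes it, and the 3% is not defined well enough for a reader to make it.

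Every participant receives active stimulation (B3.A, Overview), so no comparison group shows how often noise crosses 0.05. Applied as written, the rule can report scan noise in a patient as an effect of tACS. Amyloid reduction is Specific Aim 2, and the study is meant to supply an initial signal for later trials.

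The second route to a response, slower accumulation, has a further problem: one baseline and one follow-up scan give no pre-treatment slope to compare with.

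**Working it through.** **No figure to reproduce.** The 0.05 comes from natural-history rates. The plan states no false-positive rate and no derivation from the 3%.

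**Inputs from B3.B.** Threshold 0.05; relative error 3%; SUVR 1.6; natural rise 0.05 per year; 5 to 6 completers.

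**Assumptions not in the plan.** Normal error proportional to SUVR; a second SUVR level of 2.0; a scan gap of 3 to 6 weeks; source-study intervals of 1 and 2 years.

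**Step 1. Error in SUVR units.** 0.03 × 1.6 = 0.048 (0.060 at 2.0).

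**Step 2. SD of the two-scan difference and chance of a false fall.** With no true change, P(fall > 0.05) = 1 − Φ(0.05/SD). Values at SUVR 2.0 are in brackets.

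| Meaning of 3% | SD of difference | P(fall > 0.05) | Expected among 5 to 6, at 1.6 |
|---|---|---|---|
| SD of the difference | 0.03S = 0.048 (0.060) | 14.9% (20.2%) | 0.74–0.89 |
| Per-scan SD | √2 × 0.03S = 0.0679 (0.0849) | 23.1% (27.8%) | 1.15–1.38 |
| Per-scan 95% limit | √2 × 0.03S/1.96 = 0.0346 (0.0433) | 7.4% (12.4%) | 0.37–0.45 |
| 95% limit of the difference | 0.03S/1.96 = 0.0245 (0.0306) | 2.1% (5.1%) | 0.10–0.12 |

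At SUVR 1.6, the chance of at least one false exceedance among 5 (or 6) patients, 1 − (1 − p)^n, runs from 10% (12%) in the last row to 73% (79%) in the second.

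**Step 3. Does the rarity of yearly falls rule out the larger errors?** Over an interval of T years, P(annualised fall > 0.05) = Φ(−(0.05 + drift) × T/SD). At SUVR 1.6, for the two SD readings (SD of the difference, then per-scan SD):

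- Drift 0.05 per year with T = 1, or no drift with T = 2: Φ(−0.10/SD) = 1.9% and 7.0%.
- No drift with T = 1: Φ(−0.05/SD) = 14.9% and 23.1%.

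In the first case, yearly falls look rare although the same noise gives 15% or 23% over a few weeks. In the second, they would not be rare. The documents give neither the source intervals nor a figure for how rare such falls are.

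**Step 4. Older baseline scan.** B3.A (Study Design) allows a previously obtained scan. At 6 months with a rise of 0.05 per year, P = 1 − Φ(0.075/SD) = 5.9% and 13.5% for the two SD readings (10.6% and 18.8% at 2.0).

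**Step 5. Slower accumulation.** Expected rise is 0.05 × 3/52 = 0.003 to 0.05 × 6/52 = 0.006, roughly a tenth of the threshold or less. Slowing cannot be seen in one pair of scans on that scale.

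**Step 6. Does the 3% apply here?** Change is assessed in the stimulated target region (B3.A, Follow Up Visit) with florbetapir or florbetaben (B3.A, PET). The reference titles for the 1.6 cut-off and for two of the four yearly-change sources name PiB. The title of the source of the 3% names no tracer. Nothing in the plan shows that 3% holds for these tracers or for a regional target.

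**The case against.** **The range depends on the chosen readings.** This is true. If 3% is a mean absolute difference between scans, the SD is 0.048 × √(π/2) = 0.0602 and the rate at SUVR 1.6 is 20%. If it is a per-scan mean absolute error, the SD is √2 × 0.0602 = 0.0851 and the rate is 28%. Under the most favourable reading, 0.05 is defensible at 1.6. These points show that the rate is unknown, not that it is acceptable.

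**Rarity of yearly falls already includes scan error.** It does, and it is indirect evidence. The plan itself says that accumulation levels off in patients like these, and with no drift over one year the high-noise readings would fit poorly with rare falls. Step 3 shows that other plausible intervals and drifts fit well, so the argument does not settle the matter.

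**The intraclass correlation of 0.99 implies small error.** It does not fix the error without a between-patient SD, which the plan omits. With SD of difference = √2 × √0.01 × total SD, an assumed total SD of 0.2 to 0.5 gives 4% to 24%.

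**An earlier scan could support a judgement of slowing.** B3.A (PET) allows an earlier scan as a progression measure, but gives no method.

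**The stakes are low.** This is a small safety and feasibility pilot, the wording is hedged, the paired t-test estimates its own error, and no go/no-go decision rests on 0.05. This stands and limits the severity, but the individual comparison is still a stated way of evaluating amyloid.

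**Conclusion.** The concern holds. The plan gives no support for treating an individual fall above 0.05 as a reliable tACS effect. At SUVR 1.6, noise alone would produce one in 2% to 23% of unchanged patients across the four readings of 3% (5% to 28% at an assumed 2.0). Three of the four exceed 5% at 1.6. These rates rest on normal, proportional error and no true change over a short interval; an older baseline scan with natural rise lowers them.

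The finding is not that 0.05 fails under every reading. It is that the 3% is undefined, the comparison is missing, and a single-arm design cannot supply it. The slower-accumulation route is not usable from two scans. The group t-test is unaffected. This should be fixed, with the harm confined to per-patient claims.

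**What to change.** 1. State what the 3% measures, and confirm or qualify it for the tracer and target regions used.
2. Replace 0.05 with a limit derived from the SD of the two-scan difference and scaled to the patient's SUVR. One example is 1.645 × SD, a one-sided 5% per patient. At SUVR 1.6 this is 0.079 if 3% is the SD of the difference, 0.11 if a per-scan SD and 0.057 if a per-scan 95% limit.
3. Keep 0.05 only if 3% is shown to be a 95% limit of the difference. It then holds 5% per patient up to SUVR 0.05/(1.645 × 0.03/1.96) = 1.99.
4. Report the number of patients beyond the limit beside the number expected from noise. Do not attribute a single exceedance to tACS: even at 5% each, at least one arises by chance with probability 1 − 0.95^5 = 23% or 1 − 0.95^6 = 26%.
5. Do not count slower accumulation as a response from one baseline and one follow-up scan. Use it descriptively, and only where an earlier scan gives a pre-treatment slope.
6. Reconcile the scan count: B5 (PET) counts three amyloid scans, while B3.A describes one baseline and one follow-up.

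The cost is a change of SAP wording plus a check of the source of the 3%. If no error figure exists for these tracers and regions, state the value as an assumption and show the range. The downside is that a true individual fall between 0.05 and the new limit would not be flagged.

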Specific Aim #2: To demonstrate that 10 sessions of 40 Hz tACS stimulation decreases amyloid levels on PET imaging in patients with mild AD.

We hypothesize that 40 Hz tACS will result in a significant decrease in amyloid burden in the stimulated area.

Specific Aim #3: To demonstrate that 10 sessions of 40 Hz tACS stimulation improve resting-state EEG background activity, EEG connectivity, and performance on cognitive testing.

We hypothesize that 40 Hz tACS will result in a normalization of brain activity with increased high frequency (gamma) EEG activity and increased brain network connectivity, and that these changes will be associated with an improvement in memory and general cognitive function.

Exploratory Aim 1: As an exploratory aim, we will analyze the impact of APOE (Apolipoprotein E) and BDNF (Brain Derived Neurotrophic Factor) polymorphisms on individual response to tACS (i.e. change in amyloid level and/or gamma EEG spectral power), as measured via EEG and cognitive testing. Such information will be derived via saliva samples.

Exploratory Aim 2: The response to non-invasive brain stimulation might be related to intrinsic brain properties such as brain plasticity and connectivity levels (Freitas, Farzan, & Pascual-Leone, 2013). We will collect information on plasticity levels via a combined TMS and EEG recording session; responsiveness to tACS will be assessed via a combined tACS-EEG session.

B2. SIGNIFICANCE AND BACKGROUND FOR THE STUDY

Histopathologically, AD is characterized by diffuse amyloid- β (A β) plaques and phosphorylated tau (p-tau) deposition in neurofibrillary tangles, as well as widespread neurodegeneration. Recent PET imaging studies suggest that progressive amyloid deposition can begin up to 20 years before the onset of clinical symptoms and stabilizes around the time that clinical symptoms begin to be prominent (C. R. Jack et al., 2013; C.R. Jack Jr. et al., 2010); that tau is isolated to the lateral temporal lobes without amyloid, and spreads outside the lateral temporal lobes in patients with amyloid; and that neurodegeneration and clinical symptoms are correlated with the spread of tau (Pontecorvo et al., 2017). Consequently, the evidence suggests that both amyloid and tau play a critical role in AD pathogenesis, and interventions that reliably and safely decrease the intracerebral burden of amyloid or tau could potentially be of marked clinical importance.

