tACS involves the administration of low-amplitude (< 2mA) sinusoidal electrical currents via scalp electrodes. Current will be applied in the gamma frequency (40 Hz) range to the regions of tracer uptake on the amyloid PET scan on a case-by-case basis. Although tACS is usually administered via bipolar montages using two large electrodes, such montages have poor spatial specificity. Our group has been at the forefront of efforts using multifocal (multielectrode) montages that can deliver higher amplitude and more spatially specific stimulation patterns (Ruffini, Fox, Ripolles, Miranda, & Pascual-Leone, 2014). Consequently, stimulation will be applied to the target region with maximum amyloid levels using individualized multifocal (multielectrode) montages to maximize the induced electrical current in the target region.

Stimulation will be slowly ramped up/down at the beginning/end of each stimulation session to minimize skin sensation. tACS can elicit phosphenes - a sensation of light caused by excitation of the retina by mechanical or electrical means rather than by light. Participants will be queried each day at the end of the visit to see if they experienced phosphenes. They will be informed that this may happen and will be informed that they are free to ask to stop participation if the phosphenes bother them. We anticipate that a low percent of participants will experience this sensation (10%).

B. Statistical Considerations

Sample Size Justification: Given the intrinsic difficulties in the care of AD patients and the commitment required by the multi-day tACS intervention, we expect an attrition rate higher than 20%, potentially close to 30%. We will compare individual changes in amyloid according to the aforementioned SUVR threshold. In order to get valuable pilot data about changes in PET markers, we aim to recruit up to 20 participants to account for attrition with 10 expected to enroll in the study. This would allow for a final sample of 5/6 fully characterized participants who will complete the tACS

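### The PET plan treats an individual SUVR fall above 0.05 as evidence of effect, although that is about the size of its own measurement error, and sets neither a patient count nor a ranking against the t-test

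*Combined protocol and SAP*

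**What the plan says.** Specific Aim #2 (section B1) sets out to show that tACS lowers PET amyloid: "We hypothesize that 40 Hz tACS will result in a significant decrease in amyloid burden in the stimulated area". It gives no size of effect and no number of patients.

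Section B3.B then describes the PET evaluation in two places.

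- **Sample Size Justification.** The comparison is made patient by patient: "We will compare individual changes in amyloid according to the aforementioned SUVR threshold". No threshold has been defined before that sentence. The paragraph then argues that "significant decreases in amyloid (> 0.05 units/yr) are rare, particularly in patients with MCI/AD" and concludes that "decreases above this magnitude would represent a reliable measure of tACS effect". It ends with "Changes in SUVR will be evaluated by looking at individual trajectories of amyloid change", where a qualifying change is described as "i.e. decrease in amyloid load or slowing of amyloid build-up) exceeding the threshold". Slowed build-up is given no numerical definition.
- **Data Analysis.** The next paragraph lists outcomes for group testing at the 0.05 level: "amyloid beta levels, clinical and cognitive scores, as well as brain plasticity levels, will be measured using paired-sample t-test statistics".

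Neither place says which evaluation decides Aim 2, how many patients must pass the threshold, or what follows if the two disagree. The sentence on multiplicity correction stands in the EEG paragraph, applies only where needed, and does not order the PET evaluations.

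**The concern.** The case for the threshold rests on natural history: falls of this size are rare over a year in such patients. That argument concerns true change. It leaves out the error of two scans taken weeks apart, which can produce an apparent fall when nothing has changed. The same paragraph quotes a 3% measurement error, and 3% of 1.6 is almost exactly the cutoff.

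All patients receive active stimulation (B3.A, Overview), so there is no control arm in which apparent falls from noise would also show up. With no required count and no ranking, the PET conclusion can be settled after the scans are seen. The protocol presents the amyloid signal as the first step towards later studies of sustained reduction, so a false signal would carry forward.

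**Working it through.** **Inputs**

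- Patients analysed: 5 or 6 (Sample Size Justification). This is the only planning figure for PET; no power, effect size or SD of change is given. It does not follow exactly from the stated attrition: 10 x (1 - 0.30) = 7, and 5 or 6 of 10 would need 40-50% attrition. I use 5 and 6 as stated.
- Measurement error 3% and amyloid positivity at SUVR 1.6 or more (same section). The protocol does not say what the 3% measures, so three readings are carried.
- Cutoff 0.05, read as an absolute pre-post change (assumption; the text gives it per year).
- True change zero, normal errors, patients independent (assumptions).
- Paired t-test, taken as two-sided at 0.05 (sidedness is not stated), counting only significant decreases.

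**Step 1. SD of a patient's change.** 0.03 x 1.6 = 0.048.

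- 3% is the 95% limit of the difference: 0.048 / 1.96 = 0.0245
- 3% is the SD of the difference: 0.048
- 3% is the error of one scan: 0.048 x √2 = 0.0679

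**Step 2. One patient passes by noise.** p = Φ(-0.05 / SD): Φ(-2.04) = 0.021, Φ(-1.04) = 0.149, Φ(-0.74) = 0.231.

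**Step 3. At least one of n passes.** 1 - (1 - p)^n.

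**Step 4. Passing or a significant decrease on the t-test.** 400,000 simulated trials per setting.

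| SD of change | p, one patient | At least one, n = 5 / 6 | At least one, or t-test, n = 5 / 6 |
|---|---|---|---|
| 0.0245 | 0.021 | 10% / 12% | 12% / 14% |
| 0.048 | 0.149 | 55% / 62% | 56% / 62% |
| 0.0679 | 0.231 | 73% / 79% | 73% / 79% |

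The t-test alone gives a false decrease in 2.5% of trials. Adding it to the individual rule costs at most about 2 points.

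**Step 5. Can the two evaluations disagree?** Yes, in either direction (invented data, n = 6).

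- Changes of -0.06, -0.07, +0.03, +0.04, +0.02, +0.05: two patients pass, the mean is +0.002, p = 0.94.
- Changes of -0.03, -0.04, -0.035, -0.045, -0.03, -0.04: nobody passes, p = 0.00003.

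**Step 6. Power of the t-test for a true mean fall of 0.05.** Noncentral t with parameter 0.05 x √n / SD: 43% / 54% (n = 5 / 6) at SD 0.048, and 25% / 31% at SD 0.0679. At SD 0.0245 it is above 90%.

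**Step 7. Count needed if a count is kept.** Smallest k of 6 with a binomial tail of at most 5%: 2 (0.6%), 3 (4.6%) and 4 (2.8%) for the three SDs in order.

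**Sensitivity.** SUVR 1.6 is the lowest qualifying value. At an assumed 2.0 the SDs become 0.060 (3% as SD of the difference) and 0.085 (3% per scan), and at least one patient passes in 68% / 74% and 80% / 86% of trials. If the annual rate were prorated instead, over an assumed 4 weeks, the cutoff would be 0.05 x 4 / 52 = 0.004, and noise would pass it more often still.

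**The case against.** The strongest reply is that the protocol already has a workable hierarchy. Aim 2 speaks of a significant decrease, and the only significance test listed with amyloid is the paired t-test. The trajectory text sits under the sample size heading and is framed as pilot data. On that reading the t-test is inferential and the trajectories are descriptive. This is a fair reading, but the text does not state it, and the sentence calling such falls a reliable measure of effect points the other way.

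Several stronger claims that a reader might infer are not supported:

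- *That one patient passing establishes Aim 2.* The protocol never says so. It only fails to require more. The percentages describe what happens if one is taken as enough.
- *That having two evaluations drives the error rate.* It does not; the individual rule carries nearly all of it.
- *That a mean fall of 0.05 missing significance shows the two contradict each other.* At SD 0.048 or 0.0679 such a mean gives p = 0.051-0.18 with 5 or 6 patients. That is low power.
- *That the t-test certainly covers PET.* The list says amyloid beta levels, and Aβ is also measured in CSF and blood. Aim 2 makes PET the natural reading. If PET were excluded, Aim 2 would rest on the uncounted individual rule alone.

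This is also a small safety and feasibility study with safety as its first aim, which limits the harm.

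**Conclusion.** The point holds and should be fixed, though it is not critical in a pilot. The protocol calls an individual fall above 0.05 reliable evidence of effect, sets no number of patients, and does not rank this against the t-test. These facts need no calculation.

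The size does depend on assumptions: 0.05 as an absolute change, SUVR 1.6, normal error, no true change, and one patient counted as a signal. On those terms the false-signal probability with 5 or 6 patients is 10-12%, 55-62% or 73-79%, according to what the 3% means. Even the most favourable reading is about twice 5%; the other two exceed one half. The protocol does not show which reading applies, so the range should be reported whole.

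**What to change.** - Name one Aim 2 criterion: the paired t-test on mean SUVR change in the stimulated target, reported with its 95% interval. State that the listed amyloid beta outcome includes PET SUVR.
- Present the individual trajectories descriptively, and remove the statement that a decrease above 0.05 is a reliable measure of effect.
- If a count is kept as a criterion, state the cutoff as an absolute pre-post change, say what the 3% error measures, and set the minimum by exact binomial: 2, 3 or 4 of 6 under the three readings.

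This is a change of wording with no new patients, scans or procedures, and it should be made before the follow-up PET results are seen. The real cost is that the PET claim becomes harder to make: the t-test has only about 25-54% power for a true 0.05 fall with 5 or 6 patients under the two larger SDs. A non-significant result would therefore have to be read through its interval and not as absence of effect.
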